8.5.3.5 High Resolution peripheral Quantitative Computed Tomography (HRpQCT)

Changes in baseline in the below HRpQCT parameters at each visit will be analysed using ANCOVA in the same manner as the change from baseline in Tr.vBMD (radius) on HRpQCT (see Section 8.5.2.1) across visits during the treatment period and follow-up period:

- Total vBMD
- Cortical vBMD
- Bone volume fraction (BV/TV)

-
- Peripheral to medullary trabecular bone density ratio (Met/Inn)
 - Trabecular thickness (TbTh)
 - Trabecular number (TbN)
 - Inhomogeneity
 - Cortical thickness
 - Cortical porosity
 - Cortical area ([Ct.Ar](#))
 - Total Area ([Tt.Ar](#))
 - Trabecular separation (Tb.Sp)
 - Trabecular area ([Tb.Ar](#))

Only patients in the open-label treatment arm will have assessments at Month 3 and as such at this visit no treatment comparison will be performed.

Analyses will be performed on the FAS, mFAS and PP populations.

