6.1. Overall Design

MBPS205 is a phase 2, multicentre, multinational, double-blind, dose range-finding study comparing 3 blinded doses of setrusumab (20 mg/kg, 8 mg/kg and 2 mg/kg) and an open-label treatment arm (20 mg/kg). Participants will be randomised 1:1:1:1 into the 4 treatment arms and will receive study treatment (setrusumab) for 12 months. Participants will have HRpQCT scans of their non-dominant distal radius at baseline, 3-month (for open-label participants only), 6-month and 12-month time points to determine the effect of treatment on Tr. vBMD. Following completion of the study treatment participants can receive an optional single dose of zoledronic acid and will enter 12 months follow-up period and will have visits at Months 14, 18 and 24 to establish the rate of offset of treatment effect. Participants will also receive follow-up telephone calls at Months 16 and 21. Participants can receive an optional further dose of zoledronic acid at Month 18 at the discretion of their treating physician. During the follow-up period participants will have HRpQCT scans of their non-dominant distal radius and tibia at Month 18 and Month 24. For the purposes of the study protocol 1 month is defined as 28 days.

Figure 1: MBPS205 Study Schematic

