11.3.4. Follow-Up Period Analyses

Variables will be analysed according to their scale using general methods as described above. Results will be presented overall and by initial treatment assignment. In addition, subgroup analyses will be performed for HRpQCT, DXA, vertebral radiograph, CTX-1, and P1NP based on the administration of zoledronic acid during the follow-up period (none; at Month 12; at Month 18). Also, the frequency of administration of zoledronic acid during the follow-up period will be related both to the site and to the 12 months outcome for both primary efficacy endpoints.

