2.2 Secondary objectives

The secondary objectives are:

1. To determine the dose-response relationship of Tr. vBMD to setrusumab after 12 months of treatment
2. To evaluate the onset of treatment effect
3. To evaluate the effect of setrusumab on fracture rate (peripheral, major [long-bone], and vertebral fractures)
4. To evaluate the effect of setrusumab on vertebral fractures and vertebral height
5. To evaluate the effect of setrusumab on bone mineral density (BMD)
6. To evaluate the effect of setrusumab on bone quality
7. To evaluate changes in radial Tr. vBMD on HRpQCT and bone strength FEA during the 12 months post setrusumab treatment period
8. To evaluate the effect of setrusumab on HRpQCT parameters
9. To evaluate the effect of setrusumab on body composition
10. To evaluate the effect of setrusumab on markers of bone composition
11. To evaluate the effect of setrusumab on Patient-Reported Outcomes (PROs) and Quality of Life (QoL)
12. To evaluate the pharmacokinetics (PK) of setrusumab
13. To evaluate potential induction of antidrug antibodies (ADAs) by setrusumab and their effect on safety and PK
14. To evaluate safety and tolerability of setrusumab

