3 STUDY DESIGN

3.1 General study design

MBPS205 is a phase 2, multicentre, multinational, double-blind, dose range-finding study comparing 3 blinded doses of setrusumab (20 mg/kg, 8 mg/kg and 2 mg/kg) and an open-label treatment arm (20 mg/kg).

[figure not shown]
Following a screening period lasting up to 28 days, eligible participants will be randomised 1:1:1:1 into the 4 treatment arms stratified by OI type (Type I or III/IV) and will receive study treatment (setrusumab) for 12 months. Any participants assigned to placebo according to the previous MBPS205 protocol design will be transferred to open-label 20 mg/kg treatment for 12 months.

Participants will have HRpQCT scans of their non-dominant distal radius at baseline, 3-month (for open-label participants only), 6-month and 12-month time points to determine the effect of treatment on Tr. vBMD. The primary analysis will be conducted once all data up to month 12 has been collected for the blinded treatment groups.

Following completion of the study treatment participants can receive an optional single dose of zoledronic acid and will enter 12 months follow-up period and will have visits at Months 14, 18 and 24 to establish the rate of offset of treatment effect. Participants will also receive follow-up telephone calls at Months 16 and 21. Participants can receive an optional further dose of zoledronic acid at Month 18 at the discretion of their treating physician. During the follow-up period participants will have HRpQCT scans of their non-dominant distal radius and tibia at Month 18 and Month 24.

The Study Flow Chart is presented in Figure 1.

Figure 1: Study Flow Chart

An Independent Data Monitoring Committee will monitor safety throughout the study and make recommendations on the selected dose.

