4.2 Secondary endpoints

The secondary efficacy endpoints of this study are:

1. Tr. vBMD (radius) on HRpQCT at 12 months.
2. Tr. vBMD (tibia & radius) on HRpQCT and bone strength on FEA at 6 months
3. Tr. vBMD (tibia & radius) on HRpQCT and bone strength on FEA at 3 & 6 months in the open-label treatment arm
4. Total fracture rate at 12 months
5. Peripheral fracture rate at 12 months
6. Vertebral fracture rate at 12 months
7. Long-bone fracture rate at 12 months
8. Changes in vertebral fractures and vertebral height with Genant's semi-quantitative method and 6-point quantitative morphometry from baseline at 6 and 12 months
9. Changes in lumbar, whole body, and proximal femur DXA BMD (dual-energy x-ray absorptiometry bone mineral density) (absolute and T-score) from baseline at Month 6 and Month 12
10. Changes in bone histomorphometry
11. Tr. vBMD (tibia & radius) on HRpQCT and bone strength on FEA at 18 and 24 months
12. Changes (tibial and radial) in Total vBMD, cortical vBMD, bone volume fraction (BV/TV), peripheral to medullary trabecular bone density ratio (Met/Inn), trabecular thickness (TbTh), trabecular number (TbN), inhomogeneity, cortical thickness, and cortical porosity from baseline at 6, 12, 18, and 24 months
13. Changes in Tr. vBMD (tibia) from baseline at 12, 18, and 24 months
14. Changes (tibial and radial) in Total vBMD, cortical vBMD, bone volume fraction (BV/TV), peripheral to medullary trabecular bone density ratio (Met/Inn), trabecular thickness (TbTh), trabecular number (TbN), Inhomogeneity, cortical thickness, and cortical porosity on HRpQCT and bone strength on FEA at 3 months in the open-label treatment arm.
15. Changes in body height, weight and body mass index (BMI) from baseline at 6 and 12 months
16. Changes in lean and fat body mass from whole body DXA

17. Changes from baseline at each visit in bone turnover markers and metabolic biomarkers associated with bone including:
 - Parathyroid hormone [PTH]
 - Aminoterminal propeptide of type 1 procollagen [P1NP]
 - Carboxy-terminal propeptide of type 1 procollagen [P1CP]
 - Osteocalcin [OC],
 - Bone-specific alkaline phosphatase [BSAP]
 - Carboxy-terminal telo-peptide [CTX-1]
 - Amino-terminal telo-peptide [NTX-1]
 - Receptor activator of nuclear factor kappa-B ligand [RANKL]
 - Osteoprotegerin
 - Transforming growth factor beta [TGF- β]
 - Sclerostin
 - Released C-terminal pro-peptide of Type V collagen [Pro-C5]
 - Neo-epitope of MMP-2

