8.5.4.5 Follow-up Period Subgroup Analysis

A subgroup analysis (descriptive statistics and associated ANCOVA analyses) will be performed for HRpQCT, DXA, vertebral radiograph, CTX-1, and P1NP parameters at all follow-up visits by the administration of zoledronic acid during the follow-up period (none; at Month 12; at Month 18).

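### The follow-up is meant to show how fast the effect wears off, but the SAP specifies no Month 12-referenced change in Tr. vBMD or FEA strength with a confidence interval or test

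*SAP*

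**What the plan says.** **The question.** Objective 7 in SAP 2.2 is "To evaluate changes in radial Tr. vBMD on HRpQCT and bone strength FEA during the 12 months post setrusumab treatment period". Protocol 6.1 says participants "will have visits at Months 14, 18 and 24 to establish the rate of offset of treatment effect", and SAP 3.1 gives the same purpose. The endpoint attached to the objective in SAP 4.2 is "Tr. vBMD (tibia & radius) on HRpQCT and bone strength on FEA at 18 and 24 months", with no reference time point.

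**The analysis.**
- SAP 8.1.5 defines one baseline, the last value before first dose unless stated otherwise, and one change, from that baseline.
- SAP 8.5.1 uses the same baseline value as the ANCOVA covariate, with treatment and stratum.
- SAP 8.5.2.1 (radial Tr. vBMD and FEA strength) and 8.5.3.1 (tibial Tr. vBMD) apply this model. They report by visit but do not mention the follow-up period.
- SAP 8.5.3.5 does name the follow-up period: "Changes in baseline in the below HRpQCT parameters at each visit will be analysed using ANCOVA in the same manner as the change from baseline", meaning that of radial Tr. vBMD. Its list includes total and cortical vBMD, BV/TV, thickness, number, porosity and areas, but neither Tr. vBMD nor FEA strength.
- SAP 8.5.4.5 adds a breakdown by zoledronic acid use: "A subgroup analysis (descriptive statistics and associated ANCOVA analyses) will be performed for HRpQCT" and other parameters at the follow-up visits.
- SAP 8.7.4 says only that follow-up data are analysed separately for a CSR addendum. Protocol 11.3.4 refers to general methods. It adds that the frequency of zoledronic acid use "will be related both to the site and to the 12 months outcome for both primary efficacy endpoints".

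**The concern.** Both the objective and the stated purpose of the visits ask what happens after treatment ends, so the natural reference is the end-of-treatment scan. Every specified model measures from the pre-treatment scan instead. That shows how far bone stands above its starting point at Month 18 or 24. It does not show how much was lost or kept since Month 12.

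The addendum would then report two changes from baseline side by side, and the reader would have to subtract them. The difference would carry no valid standard error. Under observed-case summaries it could also reflect who was still being scanned. A stated secondary objective, and the main purpose given for a further 12 months of visits and scans, would rest on that subtraction.

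**Working it through.** The documents give no figure for the offset, and the effect, SD and correlation in the sample size section are redacted. The check is therefore a trace of the provisions, followed by illustrations on stated assumptions.

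**1. Trace.** A Month 12 reference could appear as a second baseline, a between-visit contrast, a slope or a Month 12 covariate. None of the four is in SAP 8.1.5, 8.5.1, 8.5.2.1, 8.5.3.1, 8.5.3.5, 8.5.4.5 or 8.7.4, or in Protocol 11.3.4. The Month 12 outcome enters the follow-up analysis only in Protocol 11.3.4, where it is related to how often zoledronic acid was given. SAP 8.4.6 tabulates that use by site, treatment and overall and omits the Month 12 outcome. SAP section 9 nevertheless lists no change from the protocol.

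**2. Change from baseline does not identify the offset.** Change since Month 12 = (1 + Month 24 change) / (1 + Month 12 change) − 1. Take +2% from baseline at Month 24 (assumed):
- Month 12 at +2%: 1.02/1.02 − 1 = 0%.
- Month 12 at +6%: 1.02/1.06 − 1 = −3.8%.
- Month 12 at 0%: 1.02/1.00 − 1 = +2.0%.

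**3. Standard error.** Let s be the SD of change from baseline at both visits (assumed equal), r the correlation between the two changes (assumed) and n = 25 per arm (SAP section 5). The within-participant change from Month 12 has SE = s√(2(1−r)/n). Subtracting two means as if independent gives s√(2/n) = 0.283s. The ratio is 1/√(1−r).

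| r (assumed) | SE, paired | SE, as if independent | Ratio |
|---|---|---|---|
| 0.3 | 0.237s | 0.283s | 1.2 |
| 0.5 | 0.200s | 0.283s | 1.4 |
| 0.7 | 0.155s | 0.283s | 1.8 |
| 0.9 | 0.089s | 0.283s | 3.2 |

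**4. Different participants.** SAP 7.2.1 presents observed cases. The protocol synopsis gives participants who discontinue treatment early an end-of-treatment visit and a 60-day visit, so some may have an end-of-treatment scan but none at Month 18 or 24. If a share f leaves after Month 12 and their gain differed by k SD from the rest, the visit means shift by f × k with no change in anyone. For f = 0.2 this is 0.2 × 0.5 = 0.10 SD to 0.2 × 1.0 = 0.20 SD. It looks like gain if the leavers had gained less, and like loss if they had gained more.

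**5. Different bone region.** SAP 7.1.3.1 uses the area common to all of a participant's scans up to the final one. At the primary analysis that can be the Month 12 region, and in the addendum the Month 24 region. A Month 12 mean from the CSR and a Month 24 mean from the addendum may therefore describe different regions.

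**The case against.** The strongest reply is that the endpoint attached to objective 7 is simply the values at Months 18 and 24. In this trial effect means change from baseline, so the change remaining at those visits, set beside Month 12, is one fair reading of offset. A crude difference can be taken from the by-visit results. This stands: a reader might infer that the documents offer no information on offset, and that would be too strong. What is missing is a specified estimate with a confidence interval or test.

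Other parts of the reply also stand:
- SAP 8.5.3.5 is not itself wrong. Its parameters have change from baseline at 6, 12, 18 and 24 months as their stated endpoint (SAP 4.2, item 12).
- The participants at Months 12 and 24 overlap and differ only by missing scans. SAP 7.1.3.1 already provides a common region within one data cut.
- Protocol 11.3.4 might be read as expecting the Month 12 outcome to drive zoledronic acid use. It only plans to examine that relation.
- It is tempting to say the interval would be 41% too wide. That figure holds only at r = 0.5, which is what equal SDs and equal correlations across visits imply for unadjusted changes, and only for a subtraction that no document plans.
- Simply swapping in the Month 12 value as covariate and testing each arm's LSMean against 0 would be a poor remedy. Month 12 is post-randomisation and may depend on dose, and those LSMeans are evaluated at the pooled Month 12 mean rather than at the arm's own.

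None of this supplies the missing Month 12-referenced estimate.

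**Conclusion.** The point holds in this form: for radial Tr. vBMD and FEA strength, the variables of objective 7, the SAP specifies no change since Month 12 with a confidence interval or test. The one main analysis that names the follow-up period omits both variables.

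The effect on the results cannot be sized from the documents. The illustrations show that one Month 24 result is compatible with loss, no change or gain since Month 12. They also show that naive subtraction would give a standard error 1.2 to 3.2 times too large for r from 0.3 to 0.9, and that selective loss of 20% could shift visit means by 0.10 to 0.20 SD. Those figures rest on assumed correlations, equal SDs and assumed dropout.

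A reader might infer that the trial's main conclusion is at risk. The documents do not support that: the gap concerns a secondary objective reported in the CSR addendum and does not touch the Month 12 primary analysis. It should be corrected because the data will exist and the objective is stated.

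**What to change.** In SAP 8.7.4, with a cross-reference in 8.5.2.1:

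1. Keep all change-from-baseline analyses.
2. For Tr. vBMD and FEA strength at Months 18 and 24, add the within-participant log change from Month 12, with both values from the same common scan region. Report it by arm with a 95% CI, either as a Month 12 contrast in a repeated-measures model (arm by visit, stratum, pre-treatment baseline) or as the paired mean change by arm in participants with both scans.
3. Do not test Month 12-adjusted LSMeans by arm against 0.
4. Present the change overall and by zoledronic acid use. In SAP 8.5.4.5, adjust the zoledronic acid comparison for the Month 12 value and label it non-randomised.
5. Restore to the SAP the Protocol 11.3.4 analysis relating zoledronic acid use to the Month 12 outcome.

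The cost is one derived variable, a small amount of modelling for the addendum and no new data. Two limits remain: Month 12 adjustment reduces but does not remove confounding in the zoledronic acid comparison, and requiring both scans removes the change in composition but not informative dropout.

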Variables will be analysed according to their scale using general methods as described above. Results will be presented overall and by initial treatment assignment. In addition, subgroup analyses will be performed for HRpQCT, DXA, vertebral radiograph, CTX-1 and P1NP based on the administration of zoledronic acid during the follow-up phase (none; at Month 12; at Month 18). Also, the frequency of administration of zoledronic acid during the follow-up phase will be related both to the site and to the 12 months outcome for both primary efficacy endpoints.

HRpQCT Validation Analysis

Validation analyses to the HRpQCT measurements will be described in a separate analysis plan.

2. Schedule of Activities (SoA) Treatment Period

Procedure	Screening (up to 28 days before Day 1)	Months													Notes All visits ± 4 days.	
		Base-line	1	2	3	4	5	6	7	8	9	10	11	EOT/12		
COL1A1/COL1A2 Mutation confirmation	X															If not available, consent can be obtained and test conducted prior to main study screening
Informed consent	X															Main study consent and bone biopsy
Inclusion and exclusion criteria	X															Re-confirm at Baseline
Demography	X															
Full physical examination including height and weight	X							X							X	
Brief physical examination		X	X	X	X	X	X		X	X	X	X	X			
Past and current medical conditions	X															
Prior medications	X															In the last 2 years

Procedure	Screening (up to 28 days before Day 1)	Months													Notes All visits ± 4 days.	
		Base-line	1	2	3	4	5	6	7	8	9	10	11	EOT/12		
Serum pregnancy test (WOCBP only)	X															
Urine pregnancy tests (WOCBP)		X	X	X	X	X	X	X	X	X	X	X	X	X	X	
Safety Laboratory assessments	X	X	X	X	X			X			X			X	To be collected pre-dose	
25-OH-Vitamin D	X	X	X		X			X			X			X		
12-lead ECG	X							X						X		
Vital signs	X	X	X	X	X	X	X	X	X	X	X	X	X	X		
Randomisation		X														
Study treatment		X	X	X	X	X	X	X	X	X	X	X	X		Weight will be measured to calculate dose	
HRpQCT	X				X			X						X	M6 and M12 scans be conducted ±7days of visit M3 for open-label participants only	
DXA	X							X						X	Calcium tablets should not be taken 2 hours prior to DXA lumbar scan	

Procedure	Screening (up to 28 days before Day 1)	Months													Notes All visits ± 4 days.	
		Base- line	1	2	3	4	5	6	7	8	9	10	11	EOT/ 12		
Vertebral Radiograph	X							X							X	
Fracture Assessment & Radiograph		←-----→													Radiographs will be taken in the event of a symptomatic fracture	

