6.1 Full Analysis Set (FAS)

The Full Analysis set consists of all participants who are randomised to one of the blinded treatment arms and take at least 1 dose of study treatment. This does not include patients randomised to placebo prior to protocol amendment 4.0.

Participants will be analysed according to the randomised treatment.

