6.2 Modified Full Analysis Set (mFAS)

The Modified Full Analysis Set consists of all participants from the FAS who have sufficient cross-sectional overlap across HRpQCT scans. Subjects must have at least 70% overlap across all performed scans (either Radius or Tibia).

For all analysis utilising the mFAS population only scans with at least 70% overlap will be included for each associated location (Radius or Tibia).

Participants will be analysed according to the randomised treatment.

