8.1.1 Populations for analysis

Demographic and baseline characteristics will be summarised by the Safety population, unless otherwise stated.

Analyses of the primary efficacy endpoint and selected secondary endpoints will be performed on the FAS population and also on the mFAS, PP population and Non-restricted FAS as a sensitivity analysis.

The remaining secondary and exploratory efficacy endpoints will be analysed using the FAS and Non-restricted FAS only.

All safety and tolerability variables will be analysed using the Safety population.

PK data will be analysed using the PK population.

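### SAP 8.5.3.5 assigns the HRpQCT parameters other than Tr. vBMD only to populations without the open-label arm, the only arm scanned at Month 3

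*SAP*

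**What the plan says.** **The endpoint.** Item 14 of SAP 4.2 lists changes, at tibia and radius, in nine HRpQCT parameters, ending with "cortical porosity on HRpQCT and bone strength on FEA at 3 months in the open-label treatment arm". Protocol Section 5 has the same endpoint, under the objective on HRpQCT parameters.

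**The scans.** The HRpQCT row of the treatment-period schedule (Protocol Section 2) carries the note "M3 for open-label participants only". SAP 8.5.3.5 agrees: "Only patients in the open-label treatment arm will have assessments at Month 3". It adds that no treatment comparison will be made at that visit.

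**The populations for these parameters.** SAP 8.5.3.5 closes with "Analyses will be performed on the FAS, mFAS and PP populations".

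**The definitions.**
- SAP 6.1: "The Full Analysis set consists of all participants who are randomised to one of the blinded treatment arms". On former placebo patients, who move to open-label 20 mg/kg, it says: "This does not include patients randomised to placebo prior to protocol amendment 4.0".
- SAP 6.2: "The Modified Full Analysis Set consists of all participants from the FAS who have sufficient" overlap between scans.
- SAP 6.4 draws the PP from the FAS. Protocol 11.2 draws it from the mFAS.
- SAP 6.3 defines the Non-restricted FAS as everyone randomised and dosed, including the open-label arm.

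**The general rules.** SAP 8.1.1, 8.5 and 8.5.3 put the primary and some *selected* secondary endpoints on the FAS, mFAS, PP and Non-restricted FAS. For the rest, SAP 8.1.1 says "The remaining secondary and exploratory efficacy endpoints will be analysed using the FAS and Non-restricted FAS only", while 8.5 and 8.5.3 say FAS only. None of them names the selected endpoints.

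**The concern.** Within one section, the SAP says that the Month 3 data come from a single arm and then lists only populations that exclude that arm. A programmer who follows the list would produce Month 3 tables with no observations for these parameters. SAP 8.5.3.5 is the only section that sets out their analysis at Month 3, so no other section supplies the result.

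The participants concerned have an additional scan so that Month 3 can be studied, and the parameter changes at that visit are a stated secondary endpoint. If the gap is noticed only after unblinding, adding a population becomes a departure from the SAP, which SAP Section 1 requires to be described and justified in the CSR. The section also covers later treatment and follow-up visits, so the same list leaves out the open-label arm's values for these parameters there too.

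**Working it through.** No power formula applies. The check is a count of who can contribute a Month 3 scan to each population.

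**Inputs.** SAP Section 5 plans 25 participants on open-label 20 mg/kg and 25 on each of three blinded doses. The arm scanned at Month 3 comes from SAP 8.5.3.5 and Protocol Section 2. Population membership comes from SAP 6.1 to 6.4.

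**Reproducing the plan's total.** 3 × 25 + 25 = 75 + 25 = 100, the stated sample size.

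**Planned number with a Month 3 scan = members of the population who are in the open-label arm.**

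| Population | Arms included | Planned size | With a Month 3 scan | Listed in 8.5.3.5 |
|---|---|---|---|---|
| FAS | three blinded arms | 75 | 0 | yes |
| mFAS | subset of FAS | at most 75 | 0 | yes |
| PP | subset of FAS (SAP) or mFAS (protocol) | at most 75 | 0 | yes |
| Non-restricted FAS | all four arms | 100 | 25 | no |

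The zeros do not depend on how many former placebo patients joined the open-label arm, because SAP 6.1 excludes them from the FAS as well. The two PP definitions also give the same answer.

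**Which parameters are affected.** SAP 8.5.3.5 lists 13. Nine are those of endpoint 14. The other four (cortical, total and trabecular area, and trabecular separation) were added in the SAP.

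**Which Month 3 results are covered elsewhere.**
- Tr. vBMD (radius): SAP 8.5.2.1 shows LSMeans at each visit and repeats the analysis on the Non-restricted FAS.
- FEA bone strength: the same section repeats the analysis on the FAS, Non-restricted FAS and PP.
- Tr. vBMD (tibia): SAP 8.5.3.1 uses the same method and includes the Non-restricted FAS.

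**Result after adding the Non-restricted FAS to 8.5.3.5.** The planned number with Month 3 data for these parameters goes from 0 to 25, before dropout and missing scans.

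**The case against.** The best answer is that the intention is plain. SAP 8.5.3.5 expects Month 3 data, since it rules out a treatment comparison there. It refers to 8.5.2.1, which includes the Non-restricted FAS. SAP 8.1.2 provides a separate open-label display group, Protocol 11.3 says open-label data will be reported separately, and SAP 8.1.8 lists data for all randomised patients. The table templates, in a separate document not available here, may already show the arm.

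The general rules can also be read helpfully. Because 8.5.3.5 uses the mFAS and PP, these parameters look more like *selected* than *remaining* endpoints, and for the selected class 8.1.1, 8.5 and 8.5.3 all include the Non-restricted FAS. On that reading, the disagreement between 8.1.1 and 8.5 over the remaining class is a side issue.

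Much of this stands. It shows that the omission is probably unintended and that the data would still appear in listings. It does not close the gap. The SAP never says which endpoints are selected, and a list specific to the section would ordinarily govern over a general rule. The reference to 8.5.2.1 concerns the method, and 8.5.3.5 then gives its own populations.

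On later visits the objection has some force: item 12 of SAP 4.2, which covers these parameters at Months 6 to 24, does not single out the open-label arm, and Protocol 11.3.1 gives no population for them. The missing assignment there is secondary to the Month 3 problem.

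**Conclusion.** The gap is real and narrow. As written, SAP 8.5.3.5 yields no Month 3 observations for the HRpQCT parameters other than Tr. vBMD: 0 of about 25 planned open-label participants are in the listed populations. The open-label arm's later visits for these parameters are also unassigned. This rests on planned numbers and on the section's list being followed literally.

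Three stronger readings are tempting, and the documents do not support them:
- *All Month 3 HRpQCT analysis is lost.* Tr. vBMD at radius and tibia is analysed on the Non-restricted FAS.
- *Endpoint 14 is empty.* Its FEA component is covered by SAP 8.5.2.1, so the endpoint is incomplete.
- *The substudy can no longer show onset of effect.* Protocol Section 5 ties that objective to Tr. vBMD and FEA, both of which are covered. The affected parameters serve a different secondary objective.

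The primary analysis and the type I error are unaffected. The point merits correction because a stated endpoint is left partly without an analysis population, and the remedy is small.

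**What to change.** 1. In SAP 8.5.3.5, add the Non-restricted FAS, with the blinded and open-label 20 mg/kg arms kept separate in the 12-month analysis. This fits SAP 8.1.2, which reserves pooling for the follow-up analysis.
2. For Month 3, specify the within-arm change from baseline with its confidence interval for the open-label arm, and no treatment comparison.
3. In SAP 8.1.1, 8.5 and 8.5.3, name the *selected* secondary endpoints and give one population rule for the remaining ones. The opening of SAP Section 6 repeats the FAS-only rule and should be brought into line.
4. Optionally, repeat the open-label analysis restricted to scans with at least 70% overlap. The mFAS cannot do this for that arm because it is drawn from the FAS, but the correction does not depend on it.

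The cost is SAP wording and a few extra tables. The Month 3 scans are already in the schedule, so no new data are needed.
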